#### 6.4.2. Service storage description if applicable

Therapeutic units should not be stored above 25°C.

Any deviation in temperature must be reported to the Clinical Research Associates within 24 hours.

The treatment kits will be made available by each hospital pharmacy of the participating centers as supplies to the department (Rheumatology) so that they are available within the timeframe stipulated by the research. This supply will be traceable by the pharmacy and the department, in line with biomedical research requirements.

The storage area must have restricted, secure access.

Products must be administered immediately after preparation. This is why, in the event of non-immediate use, storage times and conditions before use are the sole responsibility of the user.

### 6.4.3. Description of patient storage, if applicable

NA

### 6.5. Inventory management, restocking and dispensing treatments

Stocks are managed by the CHD Vendée pharmacy. CHD Vendée will receive notification of inclusion and randomization via an automatic eCRF transmission.

Regular supplies will be stored in the rheumatology departments of participating centers. Follow-up of randomization notifications, together with the traceability of dispensing within the trial, will enable replenishment to be triggered.

# 7. Efficiency assessment

### 7.1. Description of the efficacy evaluation parameters

The evaluation parameters are described in chapter 4.1.

# 7.2. Methods and timetable for measuring, collecting and analyzing effectiveness evaluation parameters

The evaluation parameters are described in chapter 4.2.2.3.

# 8. Safety assessment

#### 8.1. Definitions

Vigilance	This is the monitoring of drugs, medical devices, and other healthcare products. It also involves preventing the risk of adverse effects resulting from their use, whether this risk is potential or proven,
Adverse events (AE)	Any untoward occurrence in a patient or clinical trial participant that is not necessarily related to the clinical trial treatment.
Intensity of adverse events (AE)	It will be graded according to the criteria set when the protocol was drawn up. For any event not noted in the set classification, the rating will be as follows:  1 = mild
	2 = moderate 3 = severe

	4 = life-threatening
Adverse reactions (AR)	Any untoward response for which a causal link, whatever its importance (doubtful, plausible, possible, certain), can be envisaged either with the treatment under study or with the comparator or protocol, and, for an investigational drug, whatever the dose.  For medical devices, any noxious and unintended response to a medical device, or any incident that could have resulted in such a response had an appropriate action not been taken, in a person undergoing research or in the user of the medical device, or any effect related to a failure or alteration of an in vitro diagnostic medical device that is harmful to the health of a person undergoing research.
Serious adverse events (SAE)	Any adverse effect/event that:  * results in death,  * is life-threatening,  * results in temporary or permanent disability,  * requires or prolongs the patient's hospital stay,  * causes a congenital or neonatal anomaly,  * is medically important (the list of medically important effects/events is defined by the EMA).
Unexpected adverse events (SUSAR)	An effect whose nature, severity, frequency, or course are not consistent with the product information as listed in the investigator's brochure, the Summary of Product Characteristics or as defined in the protocol.  Article R1123-46 (8°) For research involving a medicinal product, an unexpected adverse effect is any adverse effect of the product whose nature, severity, frequency, or course are not consistent with the reference safety information given in the summary of product characteristics or in the investigator's brochure when the product is not authorized. For other research involving the human body, an unexpected adverse reaction is any adverse reaction whose nature, severity or course is not consistent with information about the products, procedures and methods used in the research.
Overdose	Actual = Administration of a greater quantity of the drug (in a single or cumulative administration) than that authorized in the Summary of Product Characteristics, the investigator's brochure.  Relative = Administration of the drug at the recommended dosage, but not adapted to the individual (undernutrition, dehydration, renal failure, etc.).
Misuse	Inappropriate use in relation to relevant reference data, occurring during the care chain, exposing a given patient to a proven or potential risk, without correlative benefit
Medication error (ME)	Corresponds to the omission or unintentional performance of an act during the care process involving a medicinal

	product, which may result in a risk or adverse event for the patient.
New fact	"Any new data that may lead to a reassessment of the benefit/risk ratio of the research or of the product that is the subject of the research, to modifications in the use of this product, in the conduct of the research, or of the documents relating to the research, or to suspending or interrupting or modifying the protocol of the research or similar research."

#### 8.2. Expected adverse events (AE or SAR)

An expected adverse reaction (AR) is a reaction that has already been mentioned in the most recent version of the investigator's brochure or package insert or in the current version of the summary of product characteristics (SmPC) for medicines that already have marketing authorization.

In the context of this protocol, the expected AEs are:

- Diprostene®: The systemic adverse effects of glucocorticoids have a low risk of occurrence after local administration, given the low blood levels, but the risk of hypercorticism (fluid retention, destabilization of diabetes and arterial hypertension, etc.) and of slowing down the thalamic-pituitary-adrenal system increases with the dose and frequency of injections.

Adverse reactions common to all routes of administration:

- Risk of local infection (depending on injection site): arthritis, meningitis, epiduritis.
- Localized atrophy of muscular, subcutaneous, and cutaneous tissues.
- A few exceptional cases of tendon rupture have been reported, particularly when coprescribed with fluoroquinolones.
- Acute microcrystalline arthritis (with microcrystalline suspension) of early onset.
- Local calcifications.
- Allergic reactions: cutaneous, localized, or generalized urticaria, angioedema, anaphylactic shock.
- Flushing: headaches and flushing may occur. These usually disappear within a day or two.
- Lumbar pain, more rarely chest pain and/or hypotension occurring within minutes of injection and spontaneously reversible.
- Blood pressure surges.
- Pain at injection site
- Sinovial mini®: Associated symptoms such as pain, warmth, redness, or swelling may occur at the injection site after using Sinovial. Applying ice to the treated joint can relieve such associated symptoms. These usually subside within a short period.

#### - The protocol:

- Anxiety about randomization (not having the "effective" drug),
- Constraints related to protocol monitoring (questionnaires)

## - Preparation and administration:

- Risk of error during drug preparation (content, dose, sterility, etc.)
- Risk of pain during infiltration
- Risk of subcutaneous hematoma
- Risk of hemarthrosis
- Risk of septic arthritis or local infection
- Risk of painful flare-ups in the days following infiltration
- The pathology: if infiltrations (of CTC and/or HA) are ineffective, the progression of pain may lead to surgical treatment (arthrodesis, trapezectomy, prosthesis, etc.).

# - Auxiliary treatments: particularly analgesics and NSAIDs:

It is impossible to list co-medications precisely as patients continue to receive their usual treatments. Nevertheless, the expected AEs correspond to those listed in the respective SmPCs of the products used in their MA indication.

- Effects expected from other associated pathologies and medical history prior to the study: related to the natural progression of pre-existing concomitant diseases.

The sponsor must be notified of pregnancies, as well as errors, risks of error, misuse, overdoses, defects, and new facts, even when there are no consequences for the patient or seriousness criteria.

#### 8.3. Non-reportable serious adverse events

Certain circumstances requiring hospitalization do not fall under the "hospitalization/extension of hospitalization" severity criterion and should not be reported as an SAE. These include:

- hospitalization for a procedure, event or treatment predefined by the protocol,
- admission/extension of stay for social or administrative reasons,
- day hospital consultation,
- hospitalization for medical or surgical treatment scheduled before the start of the research or for a previously known pathology unrelated to the research and not associated with a deterioration in the patient's condition

Complications arising from the pathology

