In 2006, Fuchs reported similar results, with improvement in pain and function for both types of infiltration in a randomized study of 56 patients. Pain improvement was faster with corticosteroids (significant at 2 weeks) but slightly better with HA at 26 weeks, with a clearer functional gain for HA mainly at 6 months.

In 2008, in a 3-arm study, one of which was placebo, Heyworth made the same findings but with no significant difference with placebo. He noted an improvement in pain and function in

all 3 groups (18 to 22 patients in each), with a clearer improvement in pain for the HA group at 6 months and in function at 3 and 6 months.

Moreover, the latest study in 2015 by Montfort, concludes that "HA was more effective over time and improved functional status more markedly in patients with severe symptoms".

Concerning the number of HA infiltrations to be administered in rhizarthrosis, a French team led by Roux C showed that there was no difference between groups receiving one, two or three infiltrations at one-week intervals, in terms of neither pain nor function.

Therefore, the 2 types of infiltration appear to be effective, but with different response profiles: corticoids have a rapid analgesic and anti-inflammatory action, whereas HA has a more delayed and sustained action over time. Consequently, it seems appealing to combine these 2 treatments to obtain a synergistic effect. One study demonstrated the benefits of this combination in gonarthrosis, which was more effective on pain than hyaluronic acid alone and there was no difference in functional improvement between the two groups.

Some authors have questioned the potential clinical or histological risks of combining these two drugs, given the risk of reduced chondrocyte proliferation and increased apoptosis which could lead to chondral degradation. However, no increased risks have been reported with this combination, neither clinically nor histologically.

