## 8.4.2. Procedures for notifying the sponsor

Any SAE, regardless of the causal relationship with the trial or research treatment(s) (with the exception of those identified in the protocol as not requiring immediate reporting), must be reported:

• by fax to the sponsor: [name]

Pharmacovigilance analysis is entrusted to the CHU Nantes vigilance unit (Pharmacovigilance physician [name], [contact], or vigilance officer [name], [contact]).

All correspondence between the investigator and the vigilance unit must be copied to the sponsor at the same time.

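### The undefined last line of section 8.3 lets a hospitalised deterioration of the infiltrated joint go unnotified as a serious adverse event

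*Combined protocol and SAP*

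**What the plan says.** Section 8.3 opens by saying that certain circumstances requiring admission do not meet the hospitalisation criterion and "should not be reported as an SAE. These include" four bulleted cases. A last, unbulleted line follows: "Complications arising from the pathology". Nothing in the section defines the pathology, limits the line, or makes an exception for the infiltrated joint.

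Section 8.4.2 requires every SAE to be notified whatever its causal relationship, "with the exception of those identified in the protocol as not requiring immediate reporting". Section 8.4.3 requires any SAE to be reported once the investigator knows of it. Section 8.4.4 requires all SAEs from infiltration to the 12-month visit. Neither of these two sections mentions an exception.

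Section 8.2, in its list of expected events, has an item for the pathology. It says that if the infiltrations do not work, "the progression of pain may lead to surgical treatment", and gives arthrodesis, trapezectomy and prosthesis as examples. Other associated pathologies are a separate item.

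Section 2.2 says that some authors have questioned the combination "given the risk of reduced chondrocyte proliferation and increased apoptosis which could lead to chondral degradation". It adds that no increase in risk has been reported, either clinically or histologically.

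**The concern.** SAE notification is meant to separate two steps. The investigator notifies, and the sponsor then assesses causality and expectedness (section 8.5.1). An exemption for complications of the study disease merges them. To use it, the investigator must first decide that the event came from the disease and not from the injection. If that decision is wrong, or cannot be made, the event is not notified as an SAE and the sponsor has no SAE report to assess.

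This matters more here because treated and diseased tissue are the same joint. The hazard that section 2.2 raises for the combination, cartilage damage, could look in a single patient like progression of the osteoarthritis. What is at stake is safety notification during the trial. The primary efficacy comparison is not affected.

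**Working it through.** No arithmetic applies. The plan gives no rate for these events and no figure to reproduce. The check sets the sections side by side.

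**1. What the pathology refers to.** Section 8.3 does not say. Section 8.2 uses the same term for the study disease, with surgery on the thumb joint as its consequence, and lists other diseases separately. On the protocol's own usage the line therefore covers complications of the rhizarthrosis itself.

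**2. How far the line reaches.** The lead-in of 8.3 concerns the hospitalisation criterion. Read as the last item of that list, the line removes only that criterion. Section 8.1 has other seriousness criteria, including disability and medical importance, and these remain. Read as a free-standing line under a heading about non-reportable SAEs, it would reach further. The narrower reading is used below.

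**3. What gives it effect.** Section 8.4.2 excepts events that the protocol identifies. Its wording speaks of immediate reporting, which could suggest mere delay. Section 8.3, however, says the listed cases are not SAE reports at all, and no later SAE route is given.

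**4. The rules applied to three cases in the infiltrated joint.**

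| Case | 8.3 with 8.4.2 | 8.4.3 and 8.4.4 |
|---|---|---|
| Admission for worsening or surgery, no other seriousness criterion, attributed to the disease | Not notified | Notified if regarded as an SAE |
| The same, but also disabling or medically important | Notified on the narrower reading | Notified |
| Worsening that meets no seriousness criterion | Not an SAE; adverse event form | Not an SAE; adverse event form |

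The first row is the gap. The sections give investigators different instructions for the same event.

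**5. Who makes the causal call.** In the first row, the outcome turns on whether the investigator attributes the worsening to the disease. Section 8.4.2 otherwise makes notification independent of that judgement. Under section 8.5.1 the sponsor must assess both causality and expectedness, and records both opinions when they differ. An event withheld at the first step does not enter that process as an SAE. Expectedness is a real question here: cartilage damage is not among the reactions that section 8.2 lists for either product.

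**6. What is still captured.** Surgery is recorded over 12 months (section 4.1.2) and compared between arms (section 9.1), but no interim analysis is planned (section 9.1). Ultrasound is repeated only at 3 months (section 4.2.2.3). Other adverse events go on the observation-book form (section 8.4.4). These routes record the event, but none is stated to trigger the assessment in section 8.5.1.

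**The case against.** The strongest reply is that damage caused by treatment is, in plain words, not a complication of the disease, so the line does not cover it. Section 8.1 supports this, because it treats even a doubtful causal link as enough for an adverse reaction. The distinction is sound in principle. It helps little in practice, because the cause may not be assignable in one patient and the line puts that assignment before notification.

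A second reply is that the line is unbulleted and has no verb, so its place in the list is uncertain. That is fair, and the page layout should be checked. It still stands under the heading of section 8.3, and uncertain scope is itself a reason to clarify it.

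A third reply is that the events are recorded elsewhere. This stands in part: the gap is in notification and assessment, not in all recording.

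A reader might infer more than the documents support:

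- **That the line contradicts the bullet before it.** That bullet exempts admission for treatment scheduled beforehand or for "a previously known pathology unrelated to the research and not associated with a deterioration in the patient's condition". It reads as being about diseases other than the one under study. The two lines have different objects and do not conflict.
- **That the plan exempts the known harm of the combination.** Section 2.2 reports a question raised by some authors and says no increased risk has been found. The step from cartilage damage to admission for surgery within 12 months is inference. Section 8.2 links surgery to ineffective infiltration and pain, not to cartilage toxicity.
- **That an imbalance would stay hidden from the Supervisory Board.** Section 8.5.3 does not say which data the Board sees, so this cannot be shown. The annual report in section 8.5.2 lists only serious events likely to be associated with the study drugs, so it was never a list of all SAEs.

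**Conclusion.** The point holds in a limited form. As written, a hospitalised deterioration of the infiltrated joint can be left unnotified as an SAE on the investigator's own causal judgement. That departs from the general rule in section 8.4.2 and from the wording of sections 8.4.3 and 8.4.4.

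The conclusion rests on two readings: that the pathology in 8.3 means the study disease, as in 8.2, and that the exception in 8.4.2 refers to the list in 8.3. Both are the natural readings, but neither is spelled out.

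On the narrower reading, the affected class is confined to events that are serious only through hospitalisation. Its frequency cannot be estimated from the documents, and a numerical bound would add nothing. The flaw merits correction because it is a stated rule that withholds events from the sponsor's assessment. It does not threaten the trial's efficacy conclusions.

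**What to change.** Either delete the last line of section 8.3 or narrow it. If it is kept, it should define the pathology and say that one class is always notified as an SAE: any event that meets a seriousness criterion and involves deterioration of the infiltrated joint, or unplanned hospitalisation or surgery for it. The sponsor then assesses causality and expectedness under section 8.5.1.

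Borrowing the condition from the preceding bullet would not work, because the study disease cannot sensibly be "unrelated to the research and not associated with a deterioration in the patient's condition".

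Sections 8.3, 8.4.2, 8.4.3 and 8.4.4 should be reconciled in the same edit. Sections 8.4.3 and 8.4.4 should refer to whatever exceptions remain, and 8.4.2 should say whether an excepted event is never notified or only not notified at once.

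The cost is a short text change and a small number of additional SAE forms. Treatment, endpoints, analysis and sample size are unchanged. Sending these events to the Supervisory Board by arm would be a further design choice and is not needed to close the gap.

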## 8.4. The investigator's role

#### 8.4.1. Reporting serious adverse events

## Information to be sent to the Sponsor

Each event is described on the appropriate form ("Initial Report of a Serious Adverse Event" or "Follow-up Report of Serious Adverse Event"), as exhaustively as possible. The information to be transmitted is as follows:

- patient identification (number, code, date of birth (MM/YYYY), date of inclusion, gender, weight, height),
- intensity (severity) of EvI
- EvI severity criteria,
- EvI start and end dates,

• clear, detailed description of the AE (diagnosis, symptoms, intensity, chronology, actions taken and results) without abbreviations,

- evolution of AE,
- current illnesses or relevant patient history,
- treatments received by the patient,
- causal relationship of the AE with the investigational drug(s), comparator(s), any associated treatments, research, or other criteria.

Whenever possible, the investigator must also attach to the SAE report:

- a copy of the hospitalization or extended hospitalization report,
- if applicable, a copy of the autopsy report,
- a copy of all additional test results, including relevant negative results, together with the laboratory's normal values,
- any other document deemed to be useful and relevant.

These documents will be anonymized and bear the patient's identification number.

## 8.4.2. Procedures for notifying the sponsor

Any SAE, regardless of the causal relationship with the trial or research treatment(s) (with the exception of those identified in the protocol as not requiring immediate reporting), must be reported:

• by fax to the sponsor: [name]

Pharmacovigilance analysis is entrusted to the CHU Nantes vigilance unit (Pharmacovigilance physician [name], [contact], or vigilance officer [name], [contact]).

All correspondence between the investigator and the vigilance unit must be copied to the sponsor at the same time.

## 8.4.3. Time limit for notifying the sponsor (Article R1123-49)

As soon as the investigating physician becomes aware of any SAE, it must be reported to the study sponsor.

The investigator notifies the sponsor of all serious adverse events, adverse reactions, and serious incidents without delay after becoming aware of them. This notification is the subject of a written report and is followed by further detailed written reports, to be sent to the sponsor without delay on the day the investigator becomes aware of them.

#### 8.4.4. Notification period to the sponsor

It is the investigator's responsibility to record and report all SAEs that occur during the entire study:

- from the date of infiltration (randomization in the study),
- and until the patient's M12 visit.

In addition, regardless of how soon after the end of the study they occur, all SAEs likely to be due to the research must be reported to the sponsor if no cause other than the research can be reasonably attributed to them (for example, serious effects that may appear long after exposure to the drug, such as cancers or congenital anomalies).

## Notification of non-serious adverse events:

All other AEs will be reported on the "adverse event" form in the observation book, specifying the date of occurrence, description, intensity, duration, method of resolution, etiology, imputability and decisions taken.

